## **Objectives & Hypotheses**

To identify the neural circuits involved in ATP-dependent cough sensitization in humans by determining whether ATP-sensitive pathways in the brainstem and brain are altered in patients with chronic cough.

### **Clinical hypothesis.**

ATP contributes to the development of cough hypersensitivity in patients by enhancing the neural activations mediated by vagal pathways involving jugular ganglia sensory neurons.

## **BACKGROUND TO PROBLEM**

Chronic cough is one of the commonest clinical problems encountered by doctors both in general and hospital practice (1), that can persist for months and years. It remains a difficult problem to manage because of our poor understanding of the mechanisms underlying its initiation and persistence and the current lack of effective antitussive therapies (2). People living with chronic cough report that chronic cough impacted considerably on their daily-life activities with a significant deterioration in health-related quality of life, leading to feeling fed-up and depressed (3) Chronic cough is also a very common co-morbid problem accompanying many pulmonary (e.g. asthma, chronic obstructive pulmonary disease (COPD), bronchiectasis, idiopathic pulmonary fibrosis) and non-pulmonary (e.g. gastro-esophageal reflux disease, cardiac failure) conditions; in some patients, it exists as a distinct clinical entity termed 'refractory' or 'idiopathic' cough.

Patients with a chronic cough report that changes in ambient temperature, laughing, talking on the phone for more than a few minutes, aerosol sprays, or smoky atmospheres characteristically trigger bouts of coughing (4, 5). In a demographic profile of chronic cough in 4,500 patients attending UK specialist cough clinics (and over 10,000 patients worldwide) (6), we found a state of hypersensitivity as a key common pathophysiological characteristic (7). This has led to the Cough Hypersensitivity Syndrome (CHS) hypothesis as an underlying cause of chronic cough whereby nerves (in the airway and/ or the brain) become sensitized,

activated and perhaps damaged (neuropathic cough) by irritant factors including viral infection, chemicals and inflammation (8).

Sensory inputs from the upper and lower airways to the brainstem are relayed to higher brain regions where they are integrated in subcortical nuclei and then mapped to the cingulate, insula, orbito-frontal and somatosensory cortices in the cerebrum (9). Studies using fMRI of the human brain during challenges with inhaled airway irritants have shown these areas to be important for the different sensory and motor responses that accompany coughing. Importantly, these central neural pathways function differently in chronic cough patients (10). Thus, responses to sensory inputs are exaggerated while those needed to suppress (control) coughing are depressed. This exciting discovery has shed an entirely new perspective on problematic cough, suggesting that pulmonary conditions that lead to coughing may do so by changing the way in which the central nervous system responds to sensory inputs. The striking parallels regarding peripheral and central sensitization which link cough and pain syndromes have prompted recent collective effort to more completely understand the processes leading to these neural dysfunction (11).

Despite this important understanding of the process of CHS, the most important unmet need relates to the lack of effective antitussives. Clinically, amitriptyline and gabapentin are used as cough suppressants with central effects potentially on CHS pathways that remains to be determined, but their effect is not uniform in all patients with chronic cough (12). However, more recently, a blocker of the ATP receptor, P2X3, Gefapixant (600 mg twice a day for 14 days), has been shown to be extremely effective in suppressing the chronic cough of patients with an idiopathic cough, with a reduction in cough frequency by 75% when compared to placebo with daytime cough frequency reduced from a mean 37 coughs per hour to 11 coughs per hour (13). These results were confirmed in another randomized, double-blind, placebo-controlled, Phase 2b crossover study using lower doses of Gefapixant (50 mg, 100 mg, 150 mg and 200 mg twice daily for four days) demonstrated significant reduction in cough frequency, including at the lowest dose of 50 mg twice daily (14). However, contrasting with this positive effect of Gefapixant, studies using TRP receptor blockers such as TRPV1 and TRPA1 antagonists have failed to show any efficacy in chronic

cough patients (15-17). Therefore, the singular potent effect of Gefapixant as an antagonist of P2X3 ATP receptor in suppressing cough opens a new focus of investigation in the role of ATP and its receptor P2X3 in CHS.

## **RATIONALE**

[figure not shown]
Given that a blocker of the ATP receptor, P2X3, has been successful in inhibiting chronic cough, we wish to use this observation to understand the putative role of ATP sensitive vagal sensory neural pathways in the cough hypersensitivity syndrome. Vagal sensory neurons are located in the nodose and jugular vagal ganglia (Fig 1). Nodose neurons developmentally originate from cells within the embryological placodes (18). There are a series of placodes that form above the pharyngeal cleft during development, collectively referred to as the epibranchial placodes, and these comprise the geniculate, petrosal, and nodose placodes that eventually form the geniculate, petrosal and nodose ganglia, associated with the 7th, 9th and 10th cranial nerves. By contrast, most peripheral neurons, including the sensory neurons of the jugular and spinal dorsal root ganglia (DRG), are developmentally derived from neural crest cells (18). Jugular ganglia neurons contribute to the innervation of tissues of the head and neck and are phenotypically similar to DRG neurons, but quite distinct to nodose neurons. Because of these developmental differences, nodose and jugular afferent nerves have distinct activation profiles, central (brain) connectivity and likely serve distinct sensory functions (reviewed in (19)). Preclinical animal studies, for example, suggest that only nodose neurons are responsive to ATP even though P2X3 receptor subunits are ubiquitously expressed in neurons of both vagal ganglia. This is because only nodose neurons express P2X2 subunits needed for functional heteromeric channel assembly. Intriguingly, other stimuli of nodose neurons (such as serotonin and adenosine) do not produce much coughing. Thus, whilst stimuli (such as capsaicin) that activate both jugular and nodose vagal chemically sensitive afferents evoke cough in conscious animals and humans, nodose chemically sensitive afferent-selective stimuli (including ATP) do not reliably evoke cough, and some nodose stimuli may inhibit cough in certain circumstances (20-22). Indeed, there is a paucity of evidence that would support a role for most subtypes of nodose neurons in cough production. This, therefore, creates a

conundrum – nodose neurons don't evoke cough when activated but are responsive to ATP while jugular neurons readily evoke coughing but don't respond to ATP ordinarily.

However, it is important to note that this work has only been conducted on neurons from healthy animals, and as such how ATP dependent responses at the neuronal level changes in pulmonary disease is not entirely clear.

***Consequently, the role of nodose versus jugular afferent pathways in human chronic cough dependent upon purinergic mechanisms remains unclear.***

The differential organization of nodose and jugular neurons within the central nervous system may allow insights into the relative contribution of nodose and jugular afferent pathways in ATP-dependent cough in health and disease. Thus, axonal guidance cues under the regulation of placodal transcription factor Phox2b attract nodose terminals to the medullary regions of the nucleus of the solitary tract (nTS) (23). By contrast, the [name] group have recently shown that the neural crest derived jugular ganglia neurons have their central terminations in the trigeminal nuclear complex, in a little-known region called the

**Fig 1.** Pulmonary jugular (red) and nodose (green) vagal sensory pathways are anatomically and functionally distinct.

paratrigeminal nucleus (Pa5) (24, 25). Thus, in rats and guinea pigs injection of a retrograde tracing dye into the nTS labels only neurons in the nodose ganglia, while a comparable injection in the Pa5 labels only jugular neurons. Because of this differential brainstem wiring, the ascending pathways in receipt of nodose and jugular afferent inputs are also different (24). *Until now, this has been impossible to study in humans. Consequently, we know nothing about the neural mechanisms involved in ATP dependent cough in humans, nor do we know how these neural processes might behave in patients with chronic cough.* This issue is central to the current funding request because our team

has optimized methods for assessing cough neural circuit activation driven by ATP in humans (see preliminary data) and are positioned to make major insights into these neural processes.

### **SIGNIFICANCE OF SELECTED TOPIC**

This is an important area of research in CHS because this provides us for the first time with some clues as to the potential mechanisms for CHS. ATP is known to activate and sensitize signal transmission at sensory sites including primary afferent neurons such as airway vagal afferent nerves via its P2X3-containing trimers and P2X3 antagonists are active in many inflammatory and visceral pain models, by inhibiting inappropriate chronic signals and decreasing peripheral and central hypersensitivity (26). Discovering the mechanisms by which P2X3 contributes to CHS may not only lead to discovery of the important peripheral and central pathways where P2X3 is crucial, but also to other potential targets for therapy. This may also lead to an understanding of the role of the P2X2 component that has been implicated, and to understand how to dissociate the anti-tussive effects of Gefapixant from its hypo- or ageustic effects. Finally, our study could provide an empirical test that would predict whether an antitussive would have the capacity to work or represent a new approach to studying the efficacy of P2X3 targeting compounds, or any other anti-tussives being developed. Regardless of the future applications, the work represents cutting-edge neuroscience in the area of cough and pulmonary sensation, and this will have impact in the field.

### **PRELIMINARY DATA**

#### *Peripheral effects of ATP via P2X3 receptors*

ATP has been shown to be a tussive agent particularly on chronic cough patients who were more sensitive than non-cough subjects to inhaled ATP (27). ATP has been shown to augment the cough response to capsaicin in patients with asthma (28). Gefapixant at a single oral dose of 50 mg did not modulate capsaicin cough responses in normal volunteers and chronic cough subjects while inhibiting ATP-induced cough particularly in chronic cough

subjects (22). These observations would suggest that ATP has a direct effect on the sensory neurons that evoke coughing through the activation of P2X3 receptors (detailed above).

*The use of fMRI to provide insights into the peripheral and central sites of activation by ATP/P2X3 activation*

We have generated functional brain imaging (fMRI) data to suggest that the different brain circuits in receipt of nodose and jugular ganglia neuron inputs (as identified in animal studies) are conserved in humans. When inhaled, the tussigenic compound capsaicin (from hot chili peppers) indiscriminately stimulates both nodose and jugular chemosensitive afferents and we have published that capsaicin inhalation produces brain activations in the primary sensory, anterior and mid-insula, cingulate, premotor, motor and orbitofrontal cortices (29, 30). These regions are presumed to encode perceptual awareness of airway irritation, and the associated emotional, cognitive and behavioral (motor) consequences. For example, activity in the human primary sensory cortex (which receives jugular ganglia inputs in animal studies) correlates with an individual's perception of airway irritation (their perceived need/ urge to cough) while activity in the insula (in receipt of nodose inputs) relates closely to the actual magnitude of the delivered stimulus independent of perception. We have now built upon these published findings by using high resolution brainstem fMRI during the inhalation of ATP (expected to only activate P2X2/3 expressing nodose-derived airway afferents) versus capsaicin (expected to activate both jugular and nodose chemosensitive afferents). Our results are striking and reveal that ATP inhalation evokes an increased signal level in the brainstem regions corresponding to the nTS, while capsaicin inhalation produces activations in both the nTS and in an area of the dorsal spinal trigeminal nucleus on the lateral margins of the brainstem that contains the paratrigeminal nucleus (Fig 2). Indeed, our healthy participants did not cough as much to ATP compared to capsaicin, consistent with studies of cough in animals and humans and the relatively poor cough-evoking properties of ATP in healthy humans (20, 21). However, the perception of airway irritation was identical between ATP and capsaicin stimuli (Fig 3). We believe that cough production will ultimately be dependent upon activation of the neural circuit that integrates in the paratrigeminal nucleus (i.e. the jugular afferent pathway) and therefore

***we hypothesize that there is an upregulation of the capacity of ATP to act via jugular ganglia pathways in chronic cough patients.***

The fMRI studies described above provide an exciting opportunity to assess for the first time which primary airway afferent pathways are likely excited or sensitized by ATP and, in turn, what aspects of the central processing of airway sensory information is altered by ATP. We have reported previously that patients with chronic cough display functional brain responses consistent with a state of central sensitization (10) that closely resembles the central sensitization accompanying chronic pain (31).

***We will extend upon these findings by determining whether ATP-sensitive pathways in the brainstem and brain are altered in patients with chronic cough, and in doing so provide insight into whether ATP effects vagal afferent processing through an interaction with nodose and/ or jugular neural pathways.***

[figure not shown]

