### **Study Design**

The study will involve 25 participants with cough hypersensitivity and 25 age and sex matched healthy controls. All participants will provide written informed consent to participate in the study, which will be approved by the Melbourne Health Human Research Ethics Committee (Australia). Before inclusion, all participants undergo screening interviews to ascertain their eligibility for the study. All participants will be non-smokers with no history of neurological disease or any recent history (over 8 weeks) of acute respiratory infections. Cough hypersensitive participants will be recruited from respiratory specialist clinics and included if they have experienced chronic cough (coughing for over 8 weeks) and are considered idiopathic/ refractory coughers (to avoid the confounds of heterogeneity of precipitating diseases). Healthy control participants will have no history of chronic respiratory disease and will be individually age and sex matched to each cough hypersensitive participant.

Participants will attend two experimental sessions. The first is used to ascertain their individual sensitivities and tolerances to inhaled challenges with capsaicin and ATP

(psychophysical testing session) and the second to determine their brain responses to challenge stimuli (brain imaging session). This is not an interventional study but rather a comparison between responses in healthy control participants versus patients with chronic cough syndrome.

All participants will first undergo a psychophysical testing session where their level of sensitivity to capsaicin and ATP is measured using a method of limits approach. The following measures of sensitivity are determined: stimulus dose evoking 2 coughs (C2), the stimulus dose required for the initial detection of an urge to cough (Cu) and the maximal suppressive stimulus dose where a participant can resist coughing (Smax). Patients will provide subjective measures of their urge-to-cough using an eleven point numerical rating scale (0, no urge-to-cough; 10, maximum urge-to-cough) evoked by single breath challenges with tussive stimuli. The capsaicin and ATP solutions are nebulized to participants via a

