### *Statistical Methods*

Statistical analysis of psychophysical parameters will be performed with SPSS 22.0. Independent t- tests will be used to test the effects of group on C2, Cu and Smax thresholds. A repeated-measures ANOVA is used to test the effects of group, dose and their interaction on urge-to-cough ratings in response to random stimulus challenges. Independent t-tests will be used to assess group effects on capsaicin/ ATP doses and urge-to-cough ratings associated with the fMRI scanning.

fMRI image analysis will be performed with FEAT, version 5.98. Regressors for each dose of capsaicin/ ATP and rating events will be included in a general linear model that also includes motion parameters and confound variables to take account of physiological noise. Contrasts for capsaicin/ ATP doses will be averaged across the three scans for each participant and used in the analysis of group and between-group effects. Group contrasts include high doses for all participants (Like-Behaviour), and activation levels will be tested for correlations with Cu and frequency of coughing during repeated stimulus challenges. Higher level analyses will be carried out for inter-group averaging and between-group comparisons. Z (Gaussianised T/F) statistic images are thresholded to define clusters of contiguous voxels activated at a significance level of  $Z > 2.3$ . To correct for multiple comparisons, a corrected cluster probability threshold (based on Gaussian Random Field Theory of  $p < 0.05$ ) is applied. Between-group contrasts are made using two different comparisons: i) during the inhalation of Smax for all individuals in both groups (matched urge-to-cough sensation). Activation levels associated with Smax doses are tested for relationships with the Cu threshold and the frequency of coughing during the psychophysical sessions.

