### *Power/Sample Size*

Sample size estimates have been made using BOLD signal changes extracted from regions of interest in the data set shown in Figure 2 and analyzed with fMRIpower (32). Inclusion of 25 participants will provide at least 80% power to detect a between-group difference of 0.48 to 0.72 standard deviation units (analogous to Cohen's d) in the regions of interest. This is sufficient power to resolve significant effects of disease (chronic cough) on ATP and capsaicin evoked brain activations in brainstem nuclei (as shown in Figure 2, data collected from n=24 with one additional participant excluded because of excessive head movement during scanning). Males and females will be included in the study.

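### The nodose-or-jugular question is judged only by thresholded clusters, with no estimate or confidence interval for either nucleus, so a null paratrigeminal result cannot show that the jugular pathway is not engaged

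*Combined protocol and SAP*

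**What the plan says.** **The question.** The fMRI part of Preliminary Data says the study will "provide insight into whether ATP effects vagal afferent processing through an interaction with nodose and/ or jugular neural pathways". The same section ties each pathway to a place in the brainstem: nodose input to the nTS, and jugular input to an area of the dorsal spinal trigeminal nucleus that contains the paratrigeminal nucleus. It describes the healthy pilot result by which areas were active: "ATP inhalation evokes an increased signal level in the brainstem regions corresponding to the nTS, while capsaicin inhalation produces activations in both the nTS and" the paratrigeminal area. The hypothesis is directional: ATP gains access to the jugular pathway in patients.

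**The analysis.** Statistical Methods states: "Z (Gaussianised T/F) statistic images are thresholded to define clusters of contiguous voxels activated at a significance level of" Z > 2.3. It continues: "To correct for multiple comparisons, a corrected cluster probability threshold (based on Gaussian Random Field Theory of" p < 0.05). It adds that "Higher level analyses will be carried out for inter-group averaging and between-group comparisons", and plans correlations of activation with the Cu threshold and cough frequency. It names no nTS or paratrigeminal mask, no mean signal with a confidence interval, and no criterion for calling a pathway uninvolved.

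**The sample size.** Study Design: "The study will involve 25 participants with cough hypersensitivity and 25 age and sex matched healthy controls". Power/Sample Size uses signal extracted from regions of interest and states: "Inclusion of 25 participants will provide at least 80% power to detect a between-group difference of 0.48 to 0.72 standard deviation units". Regions of interest do not reappear in the analysis.

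**The concern.** The and/or question allows three answers: nodose, jugular or both. Two of them include a statement that one pathway is not involved. A thresholded map can support a statement that a region responded. It cannot support a statement that a region did not, because a missing cluster can mean either no response or too little power. A cluster-extent rule makes this worse for a structure only a few voxels across.

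If neither group, or only the nTS, shows an ATP cluster, the report will have no figure for how large a paratrigeminal response remains compatible with the data. The clinical hypothesis could then seem refuted by a result that could easily arise when the nucleus does respond.

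**Working it through.** **1. The plan's own power figure.** Inputs: 25 per group, d = 0.48 to 0.72, power at least 80% (Power/Sample Size; alpha and sidedness are not stated). Two-sample t, noncentrality d × √(25/2), 5% level:

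| d | two-sided | one-sided |
|---|---|---|
| 0.48 | 38.3% | 51.1% |
| 0.72 | 70.4% | 80.6% |

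Only the upper end reproduces, and only one-sided. Read instead as one sample of 25, d = 0.48 gives 63.4% (two-sided) or 75.4% (one-sided). The steps below do not rely on the stated 80%.

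**2. One group, one location.** One-sample t, n = 25, noncentrality d × √25. At d = 0.5 this is 0.5 × 5 = 2.5. Z > 2.3 corresponds to one-sided p = 0.0107. The 0.5 SD response is an assumption. The only range in the documents, 0.48-0.72, is for between-group differences.

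| Test | Missed at 0.5 SD | Missed at 0.72 SD |
|---|---|---|
| One voxel, planned Z > 2.3, before any extent rule | 47.5% | 14% |
| Single region, two-sided 5% (not planned) | 33.0% | 7% |
| Single region, one-sided 5% (not planned) | 21.7% | 3% |

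For a between-group difference of 0.5 SD, 25 against 25, the misses are 59.0% (two-sided 5%) and 71.9% (Z > 2.3).

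**3. How often equal responses look like nTS alone.** Suppose both nuclei truly respond at 0.5 SD and the nTS passes Z > 2.3. The paratrigeminal location is then missed in 48%, 39%, 33% or 25% of studies for an assumed between-nucleus correlation of 0, 0.3, 0.5 or 0.7.

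**4. The full cluster rule (illustrative).** The voxel size is from Study Design: 1.88 × 1.88 × 2.5 mm = 8.84 mm³, so 7, 19 and 39 voxels are about 62, 168 and 345 mm³. The documents do not give the other inputs. Assumed: smoothness 3 to 5 mm FWHM, a search volume of about 37 × 26 × 50 mm, Gaussian noise, and a uniform 0.5 SD response in every voxel of the region. The extent threshold is the simulated 95th percentile of the largest null cluster, standing in for random field theory. It came out at about 8-10 voxels (3 mm) and 31-37 voxels (5 mm).

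| Responding region | Missed by cluster rule |
|---|---|
| 7 voxels | 97-98% |
| 19 voxels | 42-95% |
| 39 voxels | 5-73% |

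A test on the mask mean of the same data misses 0-16%. This is better than the 33.0% in step 2 because 0.5 SD here is per voxel, and averaging over the mask reduces the noise. It also assumes that the mask matches the responding region exactly.

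**5. Sensitivity to the response shape.** If 0.5 SD is instead the peak of a smooth blob (mask mean about 0.31-0.37 SD), the cluster rule misses 83-98% for 7-19 voxels and 39-93% for 39. A separate run with a uniform response gave 34-99% for 7-19 voxels and 3-77% for 39. The ranges are wide, but a region smaller than the extent threshold is nearly always missed.

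**6. What an estimate would give at n = 25.** 95% CI half-width within a group: 2.064/√25 = 0.41 SD. Between groups: 2.011 × √(2/25) = 0.57 SD.

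**The case against.** **No absence rule is written.** A reader might infer that the plan will declare ATP to act through the nodose pathway only whenever the paratrigeminal cluster is missing. The documents do not say this. The aim is worded as insight and the hypothesis is positive. This stands, and the point is confined to what a null result can support.

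**The between-group contrast guards against false recruitment.** A reader might also infer that a missed cluster in controls would make an ordinary jugular response in patients look like disease. Under the planned analysis, alteration in patients is tested by the between-group contrast. If both groups respond equally, that contrast is null in expectation, whatever the control map shows. The error would need someone to compare two separate maps instead, which Statistical Methods does not propose. This stands too. The contrast does not help when it is itself null.

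**There is a positive control.** Capsaicin is given in the same runs, and the pilot (n = 24) reports activation in the paratrigeminal area with it. The nucleus is therefore not invisible to the method, although the text gives no threshold for that result. This is a reason to report the capsaicin signal in the same mask, but it does not bound the ATP response.

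**The miss rates are assumption-driven.** It would be tempting to say that a half-SD response is missed at least a third of the time. That 33.0% belongs to a test the plan does not contain, is just under a third, and falls to 7% at 0.72 SD. The cluster figures depend on assumed smoothness, search volume, region size and response shape. They show direction and range, not the study's actual power.

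**Conclusion.** The concern holds in a limited form. The plan has a rule for saying that a nucleus responded, but no estimate or criterion that would let it say a nucleus did not. At n = 25 a null is weak evidence of absence: about 48% of studies would miss a 0.5 SD response at a single voxel, 14% at 0.72 SD, and for very small regions the extent rule raises this sharply under the stated assumptions. The study was sized on region-of-interest signal, so a region-level analysis fits its own design and is likely to be more sensitive. The documents do not support the stronger readings, that the plan commits to a nodose-only conclusion or that its between-group comparison would produce false recruitment. This is a cheap improvement to the analysis and its interpretation, not a flaw that invalidates the study.

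**What to change.** Add to Statistical Methods:

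- An nTS mask and a paratrigeminal mask, with their source stated, fixed before the group maps are viewed. The documents name no mask. If pilot data are used to draw one, those participants should not also count among the 25 controls.
- For each mask, the mean ATP-evoked and capsaicin-evoked signal in each group, and the between-group difference, all with 95% CIs.
- A statement that absent nodose or jugular involvement will not be concluded from a missing cluster. A pathway is called not engaged only if the CI excludes a margin fixed beforehand, for example a stated fraction of the capsaicin-evoked signal in that mask. Otherwise the result is reported as *not determined*.

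The whole-map analysis can stay as it is.

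**Cost.** SAP wording, two masks and signal extraction from data already planned; no extra scans or participants. The price is candour about precision. With half-widths of 0.41 SD within a group and 0.57 SD between groups, some results will be undetermined. With a margin of 0.5 SD and a true response of zero, the upper 95% limit falls below the margin in about 67% of studies (the mirror image of the 67.0% power implied by the 33.0% miss in step 2). Equivalence within ±0.5 SD, using a 90% interval, has about 57% power.
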